10.2.4.2 Treatment Visit

An eligible patient may only be treated if the patient presents with an eligible attack. The patients will remain in hospital for 4-5 hours during a treatment visit. The procedures performed at subsequent treatment visits will be the same.

Permitted deviations of actual sampling and assessment time points from those projected in the Schedule of Assessments will be within ten percent, calculated from $t = 0$ (start of study medication administration) to the relevant activity. The following procedures will be performed over a 4-5 hour period as follows:

At presentation of the attack:

- assessment of current angioedema signs and evaluation of evolution since onset of symptoms, including investigator's symptom score
- perform physical examination (including weight), assessment Tanner Stage (see [Appendix G](#))
- record vital signs (supine blood pressure, pulse, body temperature)
- assess and record changes or additions in current prescription and OTC medications, vitamins and supplements including start date, dosage, frequency, route, indication for usage since the last study visit
- assess and record if any medications previously reported as taken on an as needed basis (PRN) were taken since the onset of symptoms
- record and assess new AE/SAE's or changes to ongoing AE/SAE's since the last visit or last infusion, if applicable
- evaluate all inclusion and exclusion criteria
- 12-lead ECG
- blood sampling for routine laboratory safety parameters, PK/PD (only at first attack) and Immunological Analysis (C1INH auto antibodies (IgM and IgG anti-rhC1INH and anti-HRI) and C4.
- pregnancy test (only for post-menarcheal female patients)
- assessment of baseline angioedema signs by VAS-scales and TEQ just before infusion.

Infusion (T=0h)

- perform infusion of Ruconest

Directly following infusion (T5 min)

- blood sampling for PK (from a vein in the contra-lateral arm)

30 minutes (\pm 3 min), and 1 hour (\pm 6 min), 2 hours (\pm 12 min) and 4 hours (\pm 24 min) post-Infusion

- assessment of current angioedema signs (patient's VAS, TEQ and IS-score)
- record vital signs (supine blood pressure, pulse, body temperature)
- 12 lead ECG between 30 min and 2 hours
- blood sampling for PK/PD between 2 and 4 hours post-infusion
- record and assess new AE/SAE's or changes to ongoing AE/SAE's since infusion
- record changes in concomitant medication and/or need for rescue medication

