#### **4.1.1.2 Visual Analogue Scale (VAS)**

VAS scores on angioedema signs and symptoms are recorded repeatedly throughout the study at the following time-points; Presentation, 30 minutes, 1, 2, 4, 8 and 24 hours.

The VAS scores are measured at up to five different locations (Abdominal, Urogenital, OPL, Facial, or Peripheral Locations), depending on the affected locations.

A series of location specific VAS assessments are taken with the last VAS question for each location indicating the overall severity of angioedema symptoms as felt by the patient for that location (0 mm corresponding to 'No symptoms' and 100 mm corresponding to 'Extremely disabling'), and is called the Overall VAS score.

**Overall VAS:** The Overall VAS score is Question 4 for attacks at Facial or Peripheral Locations, Question 5 for attacks at an Abdominal location, Question 6 for attacks at an Urogenital location and Question 7 for attacks at an OPL location.

All VAS tables will be based on the Overall VAS score for a given location, the other VAS scores will be listed only.

The Baseline Overall VAS score for each location is defined as the last non-missing measurement collected/derived prior to the first study medication administration at Time 0 hours for the attack. This would normally be the Presentation Overall VAS assessment.

The change from Baseline Overall VAS score at each post-baseline time-point will be calculated as:

Overall VAS score obtained at the specific post-baseline time-point – Baseline Overall VAS score

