## **4.1.2 Primary Efficacy Measure**

### **4.1.2.1 Time to beginning of relief based on Overall VAS**

The time to beginning of relief will be assessed using the Overall VAS score, where time of beginning of relief will be assessed as the first time point at which the VAS score decreases by at least 20mm at any eligible anatomical location compared to Baseline, with persistence of the decrease at the next time point.

The time of relief will be the first time point at which the Overall VAS score decreases by at least 20mm compared to Baseline. For example, if this was achieved at 2 hours with persistence shown at 4 hours then the time of beginning of relief of symptoms will be 2 hours.

Patients who do not have beginning of relief during the time that they are followed-up will be censored at the last time at which the Overall VAS score is recorded at any eligible anatomical location. Note: If a patient was randomized but did not have any post-baseline efficacy data then they will be censored at Presentation. Patients who first have a decrease of  $\geq 20$ mm at the last time Overall VAS score was recorded will not have achieved beginning of relief with persistence. Therefore, they will be censored at the penultimate time that Overall VAS was recorded.

Time to beginning of relief (minutes) will be calculated as:

Actual date and time of first relief (or date and time of censoring) – Date and time of the Baseline Overall VAS assessment

The actual date and time of beginning of relief will be used in the calculation.

The beginning of relief assessed using Overall VAS will be assessed for the first eligible location at which time to beginning of relief of symptoms by Overall VAS first occurred. Only locations with a populated start date and time and corresponding Overall VAS will be used for the calculation of time to beginning of relief.

For the evaluation of persistence, the decrease of  $\geq 20$ mm is required at the next assessment time for which the Overall VAS score is not missing. For example, if 2 Overall VAS determinations with  $\geq 20$ mm decline from Baseline are separated by a missing scheduled assessment then beginning of relief with persistence would have still been achieved.

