#### **4.1.4.6 Therapeutic failure**

A patient will be assessed as having had a therapeutic failure if any of the following occurs:

- Time to the beginning of relief of symptoms for the attack based on the Overall VAS occurs later than 4 hours after Baseline.
- Within 4 hours after beginning of treatment administration and after beginning of relief, the Overall VAS increases again to a value of at least the Baseline score.
- The patient has occurrence of HAE at a new location within 4 hours after achieving beginning of relief of symptoms (Based on an IS score of greater than 0 at a new location that had an IS score of 0 at Baseline). Beginning of relief of symptoms here is based on the Overall VAS as defined in Section 4.1.2.1.
- The patient taking any of the medications that may interfere with the assessment of the impact of Ruconest on efficacy measures, between the onset of the attack and prior to time of initial relief of symptoms including:
  - Narcotics
  - Plasma-derived C1 inhibitor
  - Fresh frozen plasma
  - Bradykinin receptor antagonist
  - Analgesics
  - Anti-emetics
  - Non Steroidal Anti-Inflammatory Drugs (NSAIDs)
  - Paracetamol (within 45 minutes before the administration of Ruconest)

The medical monitor will perform a manual review of the concomitant medications and identify those which fall into the above categories.

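### The strict 4-hour therapeutic-failure limit falls against a 4-hour VAS that may be taken from 216 to 264 minutes, so relief first seen at that visit is classed by scoring time and by the lag from Baseline VAS to dosing

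*SAP*

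**What the plan says.** - **Failure limit.** SAP 4.1.4.6, first criterion: an attack fails if "Time to the beginning of relief of symptoms for the attack based on the Overall VAS occurs later than 4 hours after Baseline". Protocol 10.1.3 sets the same limit from baseline. Protocol Appendix F counts the 4 hours from study medication administration instead. None of the three gives a tolerance.
- **How the time is computed.** SAP 4.1.2.1: "The actual date and time of beginning of relief will be used in the calculation". The time subtracted is the "Date and time of the Baseline Overall VAS assessment".
- **What Baseline is.** SAP 4.1.1.2: the "last non-missing measurement collected/derived prior to the first study medication administration at Time 0 hours for the attack". It therefore precedes dosing.
- **When the VAS is taken.** Protocol 10.2.3 schedules it at 30 min and 1, 2, 4, 8 and 24 h. Permitted deviations (Protocol 10.2.4.2) "will be within ten percent, calculated from $t = 0$ (start of study medication administration) to the relevant activity"; for the 4-hour visit the section states this as 24 minutes either way.
- **Relapse criterion.** SAP 4.1.4.6, second criterion: "Within 4 hours after beginning of treatment administration and after beginning of relief, the Overall VAS increases again" to at least the Baseline score.
- **Nominal times.** The SAP's only nominal-time rule (6.9.2.1) concerns PK/PD summaries and boxplots.

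**The concern.** Relief can be dated only to an assessment, and there is none between 2 h and 4 h or between 4 h and 8 h. The 4-hour VAS is thus the last score that can show relief in time, and the limit sits at the nominal time of that visit with no allowance for the visit window. Suppose two children with the same response both show it first at the 4-hour visit, one scored at 238 min and the other at 245 min. Both visits comply with the protocol. If the Baseline VAS was taken less than 2 min before dosing, the first child is a success and the second a failure.

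The clock adds to this. The visit window runs from start of administration, but the limit runs from the Baseline VAS, so a lag between the two moves more compliant visits past the limit.

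At stake is the failure rate tabulated for the ITT and PP sets and charted for first and last attack. It would partly measure visit punctuality and pre-dose workflow. With about 20 patients, one reclassified patient moves the rate for an attack number by 1/20 = 5 points.

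**Working it through.** **1. The plan's own window.** Ten percent of the scheduled minutes: 30 → 3, 60 → 6, 120 → 12, 240 → 24. All four agree with Protocol 10.2.4.2. The 4-hour window is 240 ± 24 = 216 to 264 min from t = 0.

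**2. Which visits are exposed.** The 2-hour visit ends at 120 + 12 = 132 min, well under 240. The 8-hour visit, allowed 1 hour either way, starts at 480 − 60 = 420 min, well over. Only a first qualifying decrease at the 4-hour visit is affected.

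**3. Share of those first responses classed as failures.** Let L be the minutes from Baseline VAS to t = 0. Elapsed time is the visit time plus L, and the attack fails if this exceeds 240. With visit times assumed uniform over 216-264 min,

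P(failure | first response at the 4-hour visit) = min(1, (24 + L)/48).

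| L (min) | In-window range after Baseline (min) | Share classed as failures |
|---|---|---|
| 0 | 216-264 | 24/48 = 50% |
| 5 | 221-269 | 29/48 = 60% |
| 10 | 226-274 | 34/48 = 71% |
| 15 | 231-279 | 39/48 = 81% |
| 24 or more | 240-288 or later | 100% |

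An exactly punctual visit gives 240 + L, so it fails for any L > 0. If a site counts the window from the end of a 5-minute infusion, the shares are 60% at L = 0, 71% at 5 and 81% at 10, and 100% from L = 19.

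**4. How many attacks are exposed.** Neither document gives visit times or the distribution of relief times, so this step is illustrative. Assume exponential relief times, S(t) = 2^(−t/median), and scoring at nominal times. The share first showing relief at the 4-hour VAS is S(120) − S(240). The medians are from Protocol 9.3.

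| Median (min) | Source | S(120) | S(240) | Difference | Half of it |
|---|---|---|---|---|---|
| 37 | C1 1205-01 OLE, attack 3 | 0.106 | 0.011 | 9.4% | 4.7% |
| 45 | Adolescents | 0.157 | 0.025 | 13.3% | 6.6% |
| 67 | C1 1205-01 OLE, attack 5 | 0.289 | 0.083 | 20.5% | 10.3% |
| 122 | C1 1205-01 RCT, 50 U/kg | 0.506 | 0.256 | 25.0% | 12.5% |

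The last column supposes that half of these scores fall after 240 min, which is the L = 0 case in step 3.

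**5. Relapse criterion.** Relief requires persistence at the next score. For a single location, a decrease first seen at 2 h and gone at 4 h is not beginning of relief at all. The criterion can miss a relapse only when relief was seen at 30 min or 1 h, was confirmed at the next score, and was first back at baseline at a 4-hour VAS taken after 240 min. The direction is opposite to criterion 1 and the scope is much narrower.

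**6. Precision.** Clopper-Pearson 95% intervals for n = 20: 0/20 = 0% (0-16.8%), 1/20 = 5% (0.1-24.9%), 2/20 = 10% (1.2-31.7%), 4/20 = 20% (5.7-43.7%).

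**The case against.** **The criterion does not itself mention clock times.** Four hours is also a visit label in SAP Table 2, and the worked example in SAP 4.1.2.1 uses round hours. This has some weight. But criterion 1 names time to relief, and the section defining it requires actual times in the sentences around the example. The clock-time reading is the one a programmer would follow.

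**L is probably small.** A footnote to the schedule of assessments asks for the VAS immediately before infusion. That favours the upper rows of the first table, but even L = 0 leaves half.

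**The size is soft.** This stands. Under this model 25% is practically the maximum, because S(120) − S(240) = S(120) − S(120)² peaks at a median of 120 min. The open-label medians at 50 U/kg of 37 to 67 min give 9-20%. Some relief first shown at a late 4-hour VAS will also truly have begun after 240 min, so not every reclassification is pure timing.

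**Scheduled visits keep some dependence on punctuality.** Relief starting at 4 h 10 min counts as in time if scored at 4 h 15 min but not at 3 h 55 min. True, but this touches only relief starting inside the window: S(216) − S(264) = 0.017 − 0.007 = 1.0% at a median of 37 min, and 0.293 − 0.223 = 7.0% at 122. The present rule exposes 9.4% and 25.0%.

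**The consequences are limited.** Therapeutic failure is exploratory, no hypothesis is tested, the primary objective is safety, and Listing 16.2.6.1.4 shows times and failure status together. All of this stands and caps the importance of the point.

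**Conclusion.** The point holds for criterion 1. As written, compliant first responses at the 4-hour VAS are split by minutes: 50% become failures at L = 0, 71% at L = 10 min and 100% from L = 24 min, assuming uniform visit times. Across all attacks, roughly 5-13% could change class if half of these scores fall after 240 min, given exponential relief times with medians of 37 to 122 min. L, visit punctuality and the relief distribution are all assumptions.

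A reader might infer three stronger things that the documents do not support:

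- *That punctuality decides the class whichever time zero is used.* Once the Baseline VAS precedes dosing by 24 min or more, every in-window 4-hour response fails and punctuality plays no part. The origin is a second driver of misclassification in its own right.
- *That relapse under criterion 2 is distorted to a similar degree.* The persistence rule confines that error to early, confirmed relief lost at a late 4-hour score.
- *That the trial's main findings are affected.* The Kaplan-Meier analyses do not use the 4-hour limit, and the safety objective does not depend on it.

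The correction is worth making because the failure rate is tabulated and charted and will be read as evidence of efficacy.

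**What to change.** - In SAP 4.1.4.6, judge criteria 1 and 2 by the scheduled assessment. Criterion 1: no failure if relief is first shown at or before the nominal 4-hour VAS taken within its window, with persistence at the next available score. Criterion 2: relapse is a return to at least the Baseline score at any assessment up to and including that one.
- Keep actual times for the Kaplan-Meier analyses.
- Record the change from Protocol 10.1.3 in SAP 7.1. Reconcile the time origin between SAP 4.1.4.6, Protocol 10.1.3 and Appendix F.
- List the attacks whose class differs between the actual-time and scheduled-visit rules. The form attached to the SAP says the analysis is finalised. If so, the change and this list belong in the clinical study report, where SAP 7.5 places changes made after database lock.

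For a first response at an in-window 4-hour visit, the chance of failing criterion 1 through scoring time or lag falls to zero for every L. The equivalent actual-time limit would be 264 min from start of infusion, or 264 + L from the Baseline VAS.

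Cost: a few sentences, a small programming change and a documented departure from the protocol. Downside: relief beginning up to 24 min past 4 hours may count as within the limit.

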Each of the VAS instruments provides a patient assessment of the intensity of a range of symptoms pertinent to a symptomatic anatomical location. The Abdominal VAS instrument measures the patient's perceptions relating to four symptoms (illness, pain, bloatedness, and nausea), the OPL VAS instrument measures six symptoms (illness, pain, swelling, breathing, speech, and swallowing), the facial VAS instrument measure three symptoms (illness, pain and swelling), the Peripheral VAS instrument measures three symptoms (swelling, pain, and use of extremity), and the Urogenital VAS instrument measures five symptoms (illness, pain, swelling, nausea, and urination). Additionally, the last question for each attack location is an overall severity VAS for a global assessment of the intensity of the symptoms at that particular location. The wording of the overall severity VAS question is the same for each of the four anatomical location VAS instruments. Examples of the forms are attached as [Appendix B](#).

In addition to completing the VAS forms, patients will answer 3 questions related to the change in severity of their symptoms since the initial assessment. This Treatment Effect Questionnaire (TEQ) will be administered (following confirmation of eligibility) with the VAS for each symptomatic anatomical location. An example of the questionnaire is attached as [Appendix C](#)). If needed, depending on the patient's level of understanding, parents may assist in completion.

In case of a new attack location, additional forms (VAS and TEQ) will be provided for the patient/legal guardian to complete and the time will be recorded.

The patient should be observed for 4 hours in the hospital. After each assessment before discharge of the patient from clinical observation, the forms will be stored in the patient's file and will not be available for review by the patient or parent/legal guardian or investigator to preserve non-biased assessment at each time point by both the patient and study physician. The exception to this will be the moment at which the investigator judges the patient's condition well enough for discharge from the hospital, enabling the investigator to verify the patient/parent scores.

The assessment of the angioedema signs by the VAS and TEQ will be performed just before start of infusion, and at T30m, T1h, T2h, T4h, T8h and T24h after study medication infusion as shown in [Appendix A](#).

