In a diary, dispensed at discharge from the hospital, the patient will be asked to record the moment at which all angioedema symptoms at all locations have resolved (complete resolution). If needed, depending on the patient's level of understanding, parents may assist in completion.

The investigator will assess the severity of the patient's angioedema symptoms using an IS for each affected anatomical location (see example in [Appendix D](#)). In case of a new attack location, additional IS-scores will be recorded. The investigator symptoms score will be assessed at presentation of the acute angioedema attack and at 30m, 1h, 2h, and 4h after study medication infusion as shown in [Appendix A](#). All results of assessments will be documented in the CRF.

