- (1) Catheter system to be used if possible, which can be used for blood sampling and treatment administration (and a second dose if necessary), and can be left for 4 hours. In order to minimize patient distress, local, topical anesthesia may be considered before placing a catheter.
- (2) P = at presentation with an acute angioedema attack. Assessments and blood samples should be done as close as possible to the time of treatment administration; the VAS and TEQ should be completed immediately prior to study medication infusion.
- (3) The patient may be discharged after 4 hours; in that case the patient questionnaire at T8h will not be completed during hospitalization but at home by the patient/legal guardian; the questionnaire is to be returned at the Day 28 visit.
- (4) Telephone interview regarding HAE-symptoms in order to document possible therapeutic failure, or late relapse, registering localization, severity and time course.
- (5) C1INH activity, C1q, C4, ant bodies against rhC1INH (confirmation + neutralizing antibodies); C4 will be repeated at baseline of each attack.
- (6) Anti rabbit epithelium (dander) and anti cow milk IgE testing at screening. Anti rabbit epithelium (dander) IgE only is tested at the Day 28 follow-up visit of each attack and every year after screening.
- (7) IgM and IgG ant bodies against C1INH (confirmation + neutralizing) and HRI (+confirmation), and C4 (only at screening and baseline of each attack)
- (8) C1INH activity (PK) and C4 (PD), only at first attack, at baseline, directly following infusion and one additional sample within the window of 2-4 hours
- (9) If relevant, i.e. only for post-menarcheal female patients

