Acute angioedema attack at a new location will be identified as an IS score greater than 0 at any time up to (and including) 24 hours for a location that had an IS score of 0 (or missing IS score) at Baseline.

Peripheral edema:

Safety of Ruconest in 2-13 year old HAE patients

Angioedema at peripheral localizations (occurring in subcutaneous rather than submucosal tissue), i.e. not localized in the abdomen (gastrointestinal tract) and/or in the facial-oro-pharyngeal region and/or in the urogenital region ('submucosal' sites), e.g. swelling at extremities, hand, wrist, lower arm, upper arm, foot, leg, ear, chest wall, abdominal wall, neck, buttocks.

Early relapse:

Beginning of relief of symptoms by overall VAS within four hours, followed by an increase of VAS score to baseline value or higher, within the first 8 hours after baseline.

Late relapse:

Beginning of relief of symptoms by overall VAS within four hours, followed by an increase of VAS value to baseline value or higher, more than 8 hours after baseline and at most 24 hours after baseline.

Spontaneous regression:

Decrease in symptoms of angioedema scored with investigator score at $t = 0$ h compared with score at the time of initial evaluation by 1 or more at an eligible location.

Submucosal attack:

Attack with presumed or visible involvement of submucosal tissue at any of the possible eligible sites, i.e. localized in the abdomen (gastrointestinal tract), facial-oro-pharyngeal region, larynx, and/or urogenital region.

Therapeutic failure:

Time to the beginning of relief based on the VAS later than 4 hrs after study medication administration, relapse of the attack within 4 hrs, and/or occurrence of HAE at a new location within 4 hours after achieving beginning of relief of symptoms. The episode will also be considered a failure if the patient recorded taking medications that may have interfered with the assessment of the impact of Ruconest on efficacy measures, prior to time of initial relief of symptoms including: narcotics, plasma-derived C1 inhibitor, recombinant human C1 inhibitor, fresh frozen plasma (FFP), or anti-emetics.

Time to beginning of relief:

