#### **4.1.1.3 Investigator Symptom Scores**

Investigator Symptom (IS) scores are recorded repeatedly throughout the study at the following time-points:

Presentation, 30 minutes, 1, 2, and 4 hours.

The scores are measured at up to 5 different locations (Abdominal, Urogenital, OPL, Facial, or Peripheral). A 6 point ordinal scale is used to indicate the severity of the symptoms.

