#### **6.7.4 Time to Event Analysis**

Kaplan-Meier (KM) analyses will be performed for each of the time to event endpoints (time to beginning of relief and time to minimal symptoms defined using Overall VAS, IS and TEQ, and time to complete resolution). For patients who have been treated for more than one attack, KM analyses for time to beginning of relief and time to minimal symptoms using the Overall VAS score will be repeated for first and last attacks.

Patients who did not have the event of interest will be censored at their last available assessment of that endpoint. For VAS endpoints, in most cases the last available assessment will be at 24 hours post infusion, for IS endpoints it will be 4 hours post infusion.

Additionally, for each endpoint the number and percentage of patients with the event will be presented, along with estimates of the median and quartile time to events with 95% confidence intervals.

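### New-location failure is detected only by the Investigator Score, which is scheduled to 4 h after infusion, but its window runs to 4 h after relief, so onsets in the gap can go uncounted

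*SAP*

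**What the plan says.** **The rule.** SAP 4.1.4.6 makes an attack a failure on "occurrence of HAE at a new location within 4 hours after achieving beginning of relief of symptoms (Based on an IS score", which must be above 0 at a location with a Baseline IS of 0). Relief here is the beginning of relief on the Overall VAS (SAP 4.1.2.1). No other instrument is named for finding a new location.

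**The IS schedule.** SAP 4.1.1.3 gives "Presentation, 30 minutes, 1, 2, and 4 hours". Protocol 10.2.3 agrees: "The investigator symptoms score will be assessed at presentation of the acute angioedema attack and at 30m, 1h, 2h, and 4h after study medication infusion". On the last available assessment, SAP 6.7.4 says that "for IS endpoints it will be 4 hours post infusion".

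**What is collected later.** The VAS is scheduled at "Presentation, 30 minutes, 1, 2, 4, 8 and 24 hours" (SAP 4.1.1.2), and the TEQ follows the same times. Protocol 10.2.3 adds: "In case of a new attack location, additional forms (VAS and TEQ) will be provided", with the time recorded. Footnote 4 to the protocol's schedule (Appendix A) describes the 24 h call as a "Telephone interview regarding HAE-symptoms in order to document possible therapeutic failure, or late relapse, registering localization, severity and time course".

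**The protocol's definition.** In Appendix F a new location is "identified as an IS score greater than 0 at any time up to (and including) 24 hours", at a location whose Baseline IS was 0 or missing. The SAP keeps only the zero.

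**The concern.** The window and the instrument run on different clocks. The window starts at relief and lasts 4 h; the instrument stops 4 h after infusion, when the child may go home. Any positive time to relief therefore leaves a tail of the window with no scheduled IS. A child with relief at 2 h who goes home at 4 h and develops a new swelling at 5 h will normally have no IS that can record it. A new-location form or the 24 h interview may hold the information, but the rule does not look there.

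The SAP is not uniform on this. For time to minimal symptoms on the VAS (SAP 4.1.3.1), a location blank at Baseline and affected after dosing enters through its first documented Overall VAS. The same new site can thus delay minimal symptoms and stay invisible to therapeutic failure in the same attack.

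The Baseline condition works in the same direction. Protocol 10.2.3 has the IS scored for each affected location, so unaffected sites may be blank at Baseline. Read literally, the SAP could then miss a new location even while the child is in hospital.

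At stake is a failure proportion, reported by attack, that can err only in the favourable direction on this criterion.

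**Working it through.** The plan states no failure rate or new-location rate, so there is no figure to reproduce. The check sets the rule against the schedule.

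**Inputs**
- Window: from relief (time t after infusion, in hours) to t + 4 (SAP 4.1.4.6).
- Last scheduled IS: 4 h, with a tolerance of 24 min (protocol 10.2.4.2).
- 8 h questionnaire: ±1 h, so 7 h at the earliest. 24 h call: ±4 h, so 20 h at the earliest (protocol 10.2.4.2 and 10.2.4.3).
- Earlier median times to relief (protocol 9.3): 45 min in adolescents, 63 min at attack 1 of the 50 U/kg open-label extension, 122 min in the 50 U/kg arm of the randomised trial.

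**Share of the window with no scheduled IS** = (t + 4 − 4)/4 = t/4. If the last IS is taken at its late limit of 4.4 h, the share is (t + 4 − 4.4)/4.

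| Relief | Window closes | Scheduled IS left in window | Uncovered, IS at 4 h | Uncovered, IS at 4.4 h |
|---|---|---|---|---|
| 0.5 h | 4.5 h | 1, 2, 4 h | 0.5/4 = 12.5% | 0.1/4 = 2.5% |
| 1 h | 5 h | 2, 4 h | 1/4 = 25% | 0.6/4 = 15% |
| 2 h | 6 h | 4 h | 2/4 = 50% | 1.6/4 = 40% |

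At the earlier medians, with the IS at 4 h: 45/240 = 19%, 63/240 = 26%, 122/240 = 51%.

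**Relief at the 4 h visit.** Arithmetically the whole window (4 to 8 h) is uncovered. But SAP 4.1.2.1 times relief from the Baseline VAS, taken just before infusion, and uses actual times. Relief later than 4 h after Baseline is already a failure under the first criterion of SAP 4.1.4.6. A visit at 4 h after infusion or later therefore lies beyond 4 h from Baseline. Only an early 4 h visit leaves such an attack open to the new-location criterion.

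**Do the later assessments fall inside the window?** Relief at the 2 h visit, taken at its late limit of 2.2 h, closes the window at 6.2 h, before the earliest 8 h form at 7 h. The 8 h form can fall inside only when relief comes at the 4 h visit. The 24 h call never does, because the window ends by 8 h for any attack not already a failure. These sources help only by supplying an onset time.

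**Illustration, on assumed rates.** Suppose 5% to 20% of 20 first attacks have a true new-location onset in the window, spread evenly over it: 1 to 4 attacks. If all relief came at 0.5 h, between 1 × 0.125 = 0.125 and 4 × 0.125 = 0.5 would fall in the uncovered part. If all came at 2 h, between 1 × 0.5 = 0.5 and 4 × 0.5 = 2 would. Neither the rates nor the even spread comes from the documents.

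**The case against.** A reader might infer more than the documents support, in four ways.

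- *That every new swelling reported at 8 h or at the 24 h call is wrongly lost.* It is not. The criterion itself covers only 4 h after relief, in protocol 10.1.3 as in the SAP. Swellings that begin after that are excluded by design. Only onsets between 4 h and relief + 4 h are at issue.
- *That the SAP invented the IS basis.* Appendix F identifies a new location by IS, and protocol 10.1.3 refers to that appendix for its terms. The child who swells at 5 h without an IS has no identified new location under Appendix F either. The mismatch begins in the protocol, which allows IS evidence up to 24 h but schedules none after 4 h.
- *That nothing after 4 h can count.* Protocol 10.2.3 says that extra IS scores are recorded for a new location, and the SAP rule is not limited to scheduled scores. Children not fit for discharge stay in hospital, and deterioration at home is to be reported at once. Some late onsets may therefore have an IS; nothing ensures it for a child at home.
- *That failures are understated as a matter of fact.* The percentages are shares of window time, not of failures. No new-location rate is given, and an affected attack may already fail on another criterion.

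A simple remedy would also overshoot. If every undated new location on the 8 h form counted as failure, and onset were even over 4 to 8 h, then for relief at 0.5, 1 or 2 h the shares outside the window would be (8 − 4.5)/4 = 87.5%, (8 − 5)/4 = 75% and (8 − 6)/4 = 50%. The VAS forms in Appendix B ask for severity at that moment, and their text shows no onset field.

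These points narrow the concern. They do not close the gap between 4 h and relief + 4 h, or account for the dropped missing-Baseline provision.

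**Conclusion.** The point holds in this form: on scheduled data the rule cannot detect new locations that begin between 4 h and relief + 4 h, nominally 12.5%, 25% and 50% of the window for relief at 0.5, 1 and 2 h. New-location failures can be understated by this gap and never overstated. The Baseline condition works in the same direction, and SAP 7.1 does not list it as a departure from the protocol.

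The effect on the failure count cannot be computed. It depends on the unknown new-location rate, on how quickly these children respond (the medians used come from older patients), on how often unscheduled IS were taken, and on overlap with other failure criteria. Therapeutic failure is exploratory, the analysis is descriptive with no hypothesis test, and the primary objective is safety. The rule is worth correcting because it can give a wrong count, but it does not threaten the trial's main conclusions.

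**What to change.** Reconcile SAP 4.1.4.6 with Appendix F, including the 24 h limit. Count a new location if, within 4 h after relief, either:

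- the IS is above 0, at a scheduled or unscheduled assessment, at a location with a Baseline IS of 0 or missing; or
- a new-location VAS/TEQ form or the 24 h interview records symptoms with an onset time in that window.

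Put new locations first seen on the 8 h form without an onset time in a sensitivity analysis only. Report, by attack, how many windows were not fully observed.

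**Cost.** No new procedure is needed, only some programming and review of the dated records. The rule would rest partly on recalled onset times, which may be missing, and the failure rate may look less favourable. Because this adds to the protocol's own definition of a new location, it should be declared as a change. The form attached to the SAP says that the analysis has been finalised, so the place for it is the clinical study report, where SAP 7.5 sends changes made after database lock.
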